#### **4.3. Primary Endpoints Analysis**

##### **4.3.1. Definition of endpoints**

The primary efficacy measure will be evaluated at 26 weeks:

- Change from baseline in HbA1c.

##### **4.3.2. Main analytical approach**

The primary efficacy of dulaglutide 1.5 mg versus dulaglutide 0.75 mg 26 weeks will be guided by the “efficacy” estimand using the efficacy analysis set 1 (EAS1). The “efficacy” estimand, represents efficacy prior to discontinuation of investigational product and prior to initiation of rescue therapy, which is without confounding effects of rescue therapy for persistent severe hyperglycemia.

##### **4.3.3. Sensitivity Analyses**

None.

##### **4.3.4. Supplementary analyses**

None.

#### **4.4. Secondary Endpoints Analysis**

The following secondary efficacy measures will be evaluated through 26 and 52 weeks:

- Change from baseline in HbA1c (% and mmol/mol)
- Proportion of participants achieving HbA1c target of  $\leq 6.5\%$  and  $< 7.0\%$
- Change from baseline in FSG (mg/dL and mmol/L)
- Change from baseline in 6-point SMBG (mg/dL and mmol/L)

- Change from baseline in body weight (kg)

In addition, following TFLs will be created:

- Estimated LS Means of HbA1c (%) (Figure)
- Estimated LS Means of Fasting Serum Glucose (Figure)
- Summary of 6-point SMBG (mg/dL and mmol/L): 2-hr Excursion for Each Meal and Means of All Meals 2-hr Excursion Values
- Summary of 6-point SMBG (mg/dL and mmol/L): Mean of 6-point BG, All-premeals BG and All-PPBG
- Summary of 6-point SMBG (mg/dL and mmol/L): Circadian Variation in 6-point BG
- Listing of 6-point SMBG (mg/dL and mmol/L)
- Summary of All Types of 6-point SMBG (mg/dL and mmol/L) Change from Baseline Values
- Estimated LS Means of Body Weight (kg) (Figure)

#### **4.5. Tertiary/Exploratory Endpoints Analysis**

None.

#### **4.6. Safety Analyses**

All safety analyses will be conducted using both the SS1 and SS2 to assess the safety parameters through 26 and 52 weeks, unless otherwise stated.

In this study AESIs defined in the PROTOCOL (Section 8.3.3) are as follows:

- a. Hypoglycemia
- b. Severe, persistent hyperglycemia
- c. Pancreatitis
- d. C-cell hyperplasia and C-cell neoplasms
- e. Cardiovascular events
- f. Hypersensitivity reactions

##### **4.6.1. Extent of Exposure**

Treatment exposure is defined as the time from when the patient is randomized at Visit 3 and receives study drug until the patient either permanently discontinues from investigational product or completes the treatment period.

Treatment exposure will be calculated for each participant and summarized by treatment group.

Treatment exposure will be summarized and listed using safety analysis set.

The summary includes duration of exposure which will be categorized into the following groups: >0 weeks,  $\geq 26$  weeks, > 0 to < 26 weeks, (for final DBL, add  $\geq 26$  to <52 weeks, and  $\geq 52$  weeks). These categories will be summarized as frequency by treatment.

Listing of Randomization Scheme, and lot numbers of study drug will be created. Lot number will be provided upon request.

#### 4.6.2. Adverse Events

Adverse events will be coded from the actual term using the Medical Dictionary for Regulatory Activities (MedDRA) and reported by preferred term and system organ class (SOC). Selected notable AEs of interest may be reported using high-level terms. All AEs and TEAEs, defined as post-baseline events that are new events or preexisting conditions that worsened in severity after randomization, will be listed by participant and visit. Information on treatment, actual term, preferred term, severity, seriousness, and relationship to study intervention will also be reported.

Summary statistics will be provided for incidence of TEAEs, SAEs, and study discontinuation due to AEs or death during the treatment period. Counts and proportions of participants experiencing AEs will be reported for each treatment group, and Fisher's exact test will be used to compare the treatment groups.

For each PT in Summary of TEAEs by Severity, Fisher's exact test will be used for overall (mild + moderate + severe) and for severe.

#### TFLs Related to Adverse Events

Analysis	Additional Information
Summary of AEs	Overview By Treatment Group
Summary of TEAEs	By PT and Treatment Group
Summary of TEAEs	By SOC, PT and Treatment Group
Summary of TEAEs by Severity	By PT and Treatment Group
Summary of TEAEs Possibly Related to Study Drug	By PT and Treatment Group
Summary of SAEs	By PT and Treatment Group
Summary of AEs Leading to Discontinuation of Study Drug	By PT and Treatment Group
Summary of AEs Leading to Discontinuation of Study	By PT and Treatment Group
Listing of SAEs	
Listing of Deaths	
Listing of AEs Leading to Discontinuation of Study and/or Study Drug	

Abbreviations: AEs= adverse events; PT= preferred term; SAEs= serious adverse events; SOC = System Organ Class; TEAE = treatment-emergent adverse events.

#### 4.6.2.1. Deaths, Other Serious Adverse Events, and other Notable Adverse Events

The number and percentage of participants reported with an SAE during the treatment period will be summarized by treatment using MedDRA PT. A listing of SAEs will be provided.

The number and percentage of participants

[1] who permanently discontinued from study treatment due to an AE

[2] who discontinue study due to an AE (including AEs that led to death)

will be summarized by treatment using MedDRA PT. Events will be ordered by decreasing frequency in total population.

#### 4.6.3. Additional Safety Assessments

##### 4.6.3.1. Clinical Laboratory Evaluation

The clinical laboratory evaluations will be summarized as described in the table below.

Continuous values are shown with descriptive summary (without LSmeans) and p values based on the model in Section 4.1.

##### TFLs Related to Clinical Laboratory Evaluations

Analysis	Additional Information
Listing of Patients with Treatment Emergent Abnormal (3*ULN) Laboratory Results	
Listing of Patients with Treatment Emergent Abnormal (ULN and LLN) Laboratory Results	
Summary and Analysis of Numeric Laboratory Tests	By Treatment Group and Visit
Summary and Analysis of Abnormal Laboratory Results	By Treatment Group and Visit
Shift of Calcitonin from Maximum Baseline to Maximum Postbaseline	By Treatment Group
Summary of Percent Change in Lipid Measurements	By Treatment Group and Visit

Abbreviations: LLN=Lower Limit Normal; ULN=Upper Limit Normal.

Listing of Individual Laboratory Values would be created upon request.

##### 4.6.3.2. Vital Signs and Other Physical Findings

Vital signs will be summarized as described in the table below.

##### TFLs Related to Vital Signs

Analysis	Additional Information
Summary of Vital Signs	By Treatment and Visit
Listing of Patients with Abnormal Vital Signs	

Listing of Vital Signs	
------------------------	--

#### 4.6.3.3. Hypoglycemia

##### TFLs Related to Hypoglycemia

Analysis	Additional Information
Listing of Individual Hypoglycemic Episodes	
Listing of Severe/Serious Hypoglycemia Episodes	
Summary of Level 1 hypoglycemia: Glucose <70 mg/dL (3.9 mmol/L) and >= 54 mg/dL (3.0 mmol/L)	Overall Period
Summary of Level 2 hypoglycemia: Glucose <54 mg/dL (3.0 mmol/L)	Overall Period
Summary of Level 3 hypoglycemia: Severe hypoglycemia	Overall Period
Summary of Nocturnal hypoglycemia	Overall Period
Summary of Clinically significant hypoglycemia (Level 2 or 3)	Overall Period

#### 4.6.3.4. Electrocardiograms (ECG)

Descriptive summary of ECG results (PR, QRS, QT, RR, mean heart rate, and corrected QT interval (QTcF)) will be created.

##### TFLs Related to ECG

Analysis	Additional Information
Summary of ECG Results	By Treatment and Visit

Abbreviations: ECG = electrocardiogram.

#### 4.6.3.5. Special Safety Topics including Adverse Events of Special Interest

##### 4.6.3.5.1. Severe, Persistent Hyperglycemia

Following TFLs will be created. Note that if a reported AE term contains the word “severe, persistent hyperglycemia “, then it is considered as **“severe, persistent hyperglycemia”**:

##### TFLs Related to Severe, Persistent Hyperglycemia

Analysis	Additional Information
Listing of Severe, Persistent Hyperglycemia	
Summary of Severe, Persistent Hyperglycemia Leading to Rescue Therapy	By Treatment Group
Summary of Severe, Persistent Hyperglycemia	By Treatment Group

Listing of Insulin Therapy for Severe, Persistent Hyperglycemia	
Summary of Insulin Therapy for Severe, Persistent Hyperglycemia	By Treatment Group

#### 4.6.3.5.2. *Pancreatitis*

Pancreatic event is captured by the eCRF (Pancreatic Event CRF). Following summary will be created. Note that “Summary of Pancreatitis Adverse Events” and “Listing of Pancreatitis Adverse Events” only include events confirmed by adjudication. Therefore, these will not be based on MedDRA PT.

#### TFLs Related to *pancreatitis*

Analysis	Additional Information
Summary of Pancreatic Enzyme Thresholds - Amylase	By Treatment Group and Visit
Summary of Pancreatic Enzyme Thresholds - Lipase	By Treatment Group and Visit
Listing of Events That Were Sent for Adjudication. Possible Cases of Pancreatitis	
Summary of Pancreatitis Adverse Events	By Treatment Group and PT
Listing of Pancreatitis Adverse Events	

Abbreviations: PT= preferred term.

#### 4.6.3.5.3. *C-cell Hyperplasia and C-cell Neoplasms*

This will be determined by the following terms:

**High Level Terms:** Anaplastic thyroid cancer, Follicular thyroid cancer, Huerthle cell carcinoma, Medullary thyroid cancer, Papillary thyroid cancer, Poorly differentiated thyroid carcinoma, Thyroid cancer, Thyroid cancer metastatic, Thyroid cancer recurrent, Thyroid cancer stage 0, Thyroid cancer stage I, Thyroid cancer stage II, Thyroid cancer stage III, Thyroid cancer stage IV.

**PT:** Thyroid c-cell hyperplasia.

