7.1. Discontinuation of Study Intervention

In rare instances, it may be necessary for a participant to permanently discontinue (definitive discontinuation) study intervention. If study intervention is definitively discontinued, the participant will remain in the study to be evaluated for all planned efficacy and safety measurements. See the SoA (Section 1.3) for data to be collected at the time of discontinuation of study intervention and follow-up and for any further evaluations that need to be completed.

Possible reasons leading to permanent discontinuation of study intervention include:

Participant Decision

The participant requests to discontinue study intervention.

Discontinuation due to a hepatic event or liver test abnormality.

Participants who are discontinued from study intervention due to a hepatic event or liver test abnormality should have additional hepatic safety data collected via the eCRF (Section 10.5, Appendix 5). Discontinuation of the study intervention for abnormal liver tests **should be** considered by the investigator when a participant meets 1 of the following conditions after consultation with the Lilly's CRP or CRS:

- ALT or aspartate aminotransferase (AST) >8X upper limit of normal (ULN)
- ALT or AST >5X ULN for more than 2 weeks
- ALT or AST >3X ULN and total bilirubin level (TBL) >2X ULN or international normalized ratio (INR) >1.5
- ALT or AST >3X ULN with the appearance of fatigue, nausea, vomiting, right upper-quadrant pain or tenderness, fever, rash, and/or eosinophilia (>5%)
- Alkaline phosphatase (ALP) >3X ULN
- ALP >2.5X ULN and TBL >2X ULN
- ALP >2.5X ULN with the appearance of fatigue, nausea, vomiting, right quadrant pain or tenderness, fever, rash, and/or eosinophilia (>5%)

Additional circumstances in which participants will be discontinued from the study intervention include:

A participant will be discontinued from study intervention due to any of the following:

- If a participant is inadvertently enrolled and it is determined that continued study intervention would not be medically appropriate (See Section 7.2.1)
- If a participant misses 3 continuous injections
- Acute or chronic pancreatitis

- If a participant is diagnosed with an active or untreated malignancy (other than basal or squamous cell skin cancer, in situ carcinomas of the cervix, or in situ prostate cancer) after randomization
- If a participant is diagnosed with C-cell hyperplasia or medullary thyroid carcinoma (MTC) after randomization

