8.3.3. Adverse Events of Special Interest

Adverse events of special interest (AESIs) for this program include:

- a. Hypoglycemia
- b. Severe, persistent hyperglycemia

- c. Pancreatitis
- d. C-cell hyperplasia and C-cell neoplasms
- e. Cardiovascular events
- f. Hypersensitivity reactions

If a, b, c, d, e, or f are reported, sites will be prompted to collect additional details/data on the specific eCRFs.

Hypoglycemia

Participants will collect information on episodes of hypoglycemia starting from Visit 3 (Week 0) until the last study visit (ET visit or Visit 801). Participants will be trained about signs and symptoms of hypoglycemia, how to treat hypoglycemia, and how to collect appropriate information for each episode of hypoglycemia in the study according to the SoA (Section 1.3). Site personnel will enter this information into the hypoglycemia eCRF at each visit.

Investigators should use the following definitions and criteria when diagnosing and categorizing an episode considered to be related to hypoglycemia (the BG values in this section refer to values determined by a laboratory or International Federation of Clinical Chemistry and Laboratory Medicine plasma-equivalent glucose meters and strips) in accordance with the 2020 ADA position statement on glycemic targets:

Level 1 hypoglycemia

Glucose <70 mg/dL (3.9 mmol/L) and \geq 54 mg/dL (3.0 mmol/L): Level 1 hypoglycemia can alert a person to take action such as treatment with fast-acting carbohydrates. Providers should continue to counsel participants to treat hypoglycemia at this glucose alert value.

Level 2 hypoglycemia

Glucose <54 mg/dL (3.0 mmol/L): Level 2 hypoglycemia is also referred to as documented or blood glucose confirmed hypoglycemia with glucose <54 mg/dL (3.0 mmol/L). This glucose threshold is clinically relevant regardless of the presence or absence of symptoms of hypoglycemia.

Level 3 hypoglycemia

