An independent clinical endpoint committee (CEC) will adjudicate all suspected cases of acute pancreatitis. Only cases of pancreatic hyperenzymemia that undergo additional diagnostic follow-up and/or are accompanied by symptoms suggestive of pancreatitis will be submitted for adjudication. In addition, AEs of severe or serious abdominal pain of unknown etiology will also be submitted to the adjudication committee to assess for possible pancreatitis or other pancreatic disease. Relevant data from participants with acute or chronic pancreatitis and those with severe or serious abdominal pain will be entered into a specifically designed eCRF page by study site or Lilly staff. The adjudication committee representative will enter the results of adjudication in a corresponding eCRF page.

Asymptomatic elevation of serum amylase and/or lipase

Each participant will have measurements of pancreatic amylase and lipase (assessed at the central laboratory) as shown on the SoA (Section 1.3), to assess the effects of the investigational doses of dulaglutide on pancreatic enzyme levels.

Serial measures of pancreatic enzymes have limited clinical value for predicting episodes of acute pancreatitis in asymptomatic participants (Nauck et al. 2016; Steinberg et al. 2017a, 2017b). Therefore, further diagnostic follow-up of cases of asymptomatic elevation of pancreatic enzymes (lipase and/or p-amylase $\geq 3X$ ULN) is not mandated but may be performed based on the investigator's clinical judgment and assessment of the participant's overall clinical condition.

C-Cell Hyperplasia and C-Cell Neoplasms

Individuals with personal or family history of certain thyroid or nonthyroid endocrine abnormalities or certain preexisting laboratory and genetic characteristics will be excluded from the study (see Section 5.2). Participants with a personal or family history of MTC or personal history of MEN 2 syndrome, or who have serum calcitonin ≥ 20 pg/mL at study entry as determined by the central laboratory will be excluded. The assessment of thyroid safety during the study will include reporting of thyroid TEAEs and measurements of calcitonin according to the SoA (Section 1.3). The purpose of calcitonin measurements is to assess the potential of dulaglutide to affect thyroid C-cell function, which may indicate development of C-cell hyperplasia and neoplasms.

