#### TFLs Related to *C-cell Hyperplasia and C-cell Neoplasms*

Analysis	Additional Information
Summary of C-cell Hyperplasia and C-cell Neoplasms	By Treatment Group
Listing of C-cell Hyperplasia and C-cell Neoplasms	

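### The C-cell adverse event of special interest is defined by a broad thyroid cancer search and summarised without a split by type, so a non-C-cell cancer would be counted under a C-cell title

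*SAP*

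**What the plan says.** Protocol section 8.3.3 names the AESI as "C-cell hyperplasia and C-cell neoplasms", and SAP section 4.6 repeats it. The protocol gives no coding terms for it. Its text on this AESI describes thyroid safety as the reporting of treatment-emergent thyroid events together with calcitonin, and says calcitonin is measured "to assess the potential of dulaglutide to affect thyroid C-cell function, which may indicate development of C-cell hyperplasia and neoplasms". Protocol section 7.1 includes among the grounds for stopping study intervention: "If a participant is diagnosed with C-cell hyperplasia or medullary thyroid carcinoma (MTC) after randomization".

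SAP section 4.6.3.5.3 supplies the coding definition. It states that the AESI is determined by a list of 14 terms, which it labels High Level Terms, and one preferred term. The 14 begin "Anaplastic thyroid cancer, Follicular thyroid cancer, Huerthle cell carcinoma, Medullary thyroid cancer, Papillary thyroid cancer", then poorly differentiated carcinoma, and go on "Thyroid cancer, Thyroid cancer metastatic, Thyroid cancer recurrent, Thyroid cancer stage 0, Thyroid cancer stage I, Thyroid cancer stage II", followed by stages III and IV. The preferred term is "Thyroid c-cell hyperplasia".

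Two outputs are planned: the "Summary of C-cell Hyperplasia and C-cell Neoplasms", by treatment group, and a listing under the same title.

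**The concern.** The AESI is named for one cell type, but its case definition takes in thyroid cancers of other types. The SAP's wording makes the list the definition itself, not a first screen, and the section plans no step to sort the hits afterwards. The only summary carries a C-cell title and, as described, has no breakdown by type.

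The study is meant to support approval of the higher dose in Japan. A reader who takes this table at its title would read any thyroid cancer in it as a C-cell event on one of the two doses. Where events are few, a single case is the whole content of the table.

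**Working it through.** The SAP gives no figure for this AESI, so there is nothing to reproduce. The check is a count of terms, a comparison of sections, and the size of one case.

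**Step 1: classify the terms in SAP 4.6.3.5.3.** The grouping rests on ordinary pathology, which the documents do not spell out. It agrees with protocol 7.1, which pairs C-cell hyperplasia with medullary carcinoma and names no other thyroid cancer.

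| Group | Terms | Count |
|---|---|---|
| C-cell specific | medullary thyroid cancer; thyroid C-cell hyperplasia | 2 |
| Another named histology | anaplastic; follicular; Huerthle cell; papillary; poorly differentiated | 5 |
| No histology given | thyroid cancer; metastatic; recurrent; stages 0, I, II, III, IV | 8 |
| Total | 14 listed cancer terms + 1 preferred term | 15 |

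So 5 + 8 = 13 of the 15 terms are not specific to C-cells, but only the 5 point positively to a different tumour.

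**Step 2: look for a later step that removes the non-C-cell hits.**

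- Pancreatitis (SAP 4.6.3.5.2): the summary and listing of pancreatitis adverse events contain only events confirmed by adjudication.
- Cardiovascular events (SAP 4.6.3.5.4): events identified are subject to medical review.
- C-cell events (SAP 4.6.3.5.3): no adjudication or review is stated. Protocol 8.3.3 provides an eCRF section for endocrine follow-up of raised calcitonin, but the SAP definition does not use it.

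**Step 3: compare the table layouts.** The pancreatitis, cardiovascular and hypersensitivity summaries are marked as by treatment group and preferred term. The C-cell summary is marked as by treatment group only.

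**Step 4: size of one case.** The randomization targets are 390 and 195 (protocol 9.2, SAP 5). The safety sets contain only dosed participants, so these denominators are approximate.

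- 1.5 mg: 1/390 = 0.26%.
- 0.75 mg: 1/195 = 0.51%.
- SAP 4.7.1.3 repeats tables by pre-study oral drug class unless otherwise specified. In a class with 20 participants on 0.75 mg, 1/20 = 5%.

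These figures show how one case would look. They do not estimate how likely it is, because the documents give no thyroid event rate.

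**The case against.** **The protocol is not contradicted.** It gives no term list for this AESI, and section 7.1 is a rule for stopping study intervention, not a case definition. Section 8.3.3 foresees thyroid reporting wider than C-cell diagnoses. This stands: a broad search fits the protocol, and the dispute is about what the result is called.

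**Thirteen of 15 overstates the matter.** A reader might infer that all 13 are misclassifications. They are not. A medullary cancer reported only as thyroid cancer with a stage would be found only through the 8 unspecified terms, so including them is defensible as a sensitive search. Only the 5 terms with another histology put a known non-C-cell tumour into the count.

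**The layout is inferred.** The table specifications are in a separate document (SAP section 1). The layout column is also an imperfect guide: the pancreatitis summary is marked as by preferred term, while the text above it says it is not based on MedDRA preferred terms. This stands as a caution. The SAP text still gives no split by type.

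**The type can be recovered.** The AESI listing shows the same events, and SAP 4.6.2 plans event summaries by preferred term, a serious-event summary by preferred term and a serious-event listing. Protocol section 10.3.2 gives malignant cancers as an example of events usually considered serious. SAP 4.6.3.1 also plans a calcitonin shift table. This stands, and it limits the point to the title and the headline count.

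**The stakes can be inflated.** A reader might infer that one misclassified case would overturn a safety conclusion, that the true C-cell count is expected to be zero, or that a labelled class warning is at issue. The documents say none of this. They attach no decision rule to this AESI, and the only class effect they describe is pulse rate.

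**Conclusion.** The point holds as a matter of definition and presentation. As written, SAP 4.6.3.5.3 would count a thyroid cancer of a named non-C-cell histology as a C-cell event, in a summary that does not show the type, with no review step to remove it. Five of the 15 terms do this directly. Eight more bring in cases whose cell type is unknown.

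The size is modest. One case would appear as about 0.26% or 0.51% by arm, no information is lost, and no efficacy analysis is touched. The conclusion assumes that the separate table specifications follow the layout stated in the SAP, and that no unstated medical review is intended. If those specifications already split the table by preferred term, only the title and the definition need attention.

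The documents do not support the stronger reading that the plan hides the types or departs from a protocol definition.

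**What to change.** In SAP 4.6.3.5.3, keep all 15 terms as the search. Retitle the output, for example *Thyroid neoplasms and C-cell hyperplasia*, and present it by treatment group and preferred term in three blocks:

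- (a) C-cell events: medullary thyroid cancer and thyroid C-cell hyperplasia.
- (b) Thyroid cancer with histology not specified, kept separate as possible C-cell events.
- (c) Thyroid cancer of another named histology.

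Block (b) should not default to an other category. A rule that admits unspecified cancers only on histology or on the endocrine follow-up eCRF could under-count: that eCRF section covers only participants who meet the calcitonin criteria, and the documents describe no collection of histology for other thyroid cancers.

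Retitle the listing to match. Check the label High Level Terms against the dictionary and correct it if the listed terms are preferred terms.

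The cost is SAP wording and one changed table shell. The C-cell block becomes narrower than the present count, but every case stays in the same table and the primary analysis is unaffected.
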